## B. Description of Population to be Enrolled:

### Settings

The study will be conducted at the VA Eastern Colorado Health Care System (VA ECHCS) and Puget Sound VA Health Care (PSVAHCS) systems. Each health care system includes a tertiary care medical center and seven community-based outpatient clinics (CBOCs).

### Study population:

**Aim 1:** A total of 400 adult subjects will be randomized in a 1:1 ratio to one of 2 treatment arms: 1) enhanced usual care or 2) team-based palliative care intervention plus usual care. A component of the study intervention involves speaking to study subjects' informal (family) caregivers. The eligibility criteria (**Table 1**) aim to enroll Veterans with a diagnosis of CHF, ILD, or COPD who are at risk of hospitalizations or death, have poor quality of life, and are able to participate in the intervention.

**Table 1. Eligibility Criteria**

#### Inclusion Criteria

- |  | Definition   |
|--|---|
| • CHF: Diagnosis of CHF in 2 years prior to enrollment   | • Inpatient hospital diagnosis or ≥2 outpatient visits*   |
| • COPD: Diagnosis of COPD in 2 years prior to enrollment   | • Inpatient hospital diagnosis or ≥2 outpatient visits*   |
| • ILD: Diagnosis of ILD in 2 years prior to enrollment   | • Inpatient hospital diagnosis or ≥ 2 outpatient pulmonary visits **  |
| • Among those with CHF or COPD, high risk for hospitalization and death                            | • Care Assessment Need score ≥ 80   |
| • Poor quality of life   | • FACT-G score ≤ 70   |
| • Symptomatic  | • Bothered by at least one of the target symptoms: pain, fatigue, depression, shortness of breath, trouble sleeping |
| • Primary care or other provider who is willing to facilitate intervention medical recommendations | • PCP listed in Electronic medical record review or self-report   |
| • Able to read and understand English  | • Self-report   |
| • Consistent access to and able to use a standard telephone  | • Self-report   |

#### Exclusion Criteria

- |   |  |
|---|--|
| • Previous diagnosis of dementia  | • Inpatient or outpatient diagnostic code†   |
| • Active substance abuse  | • Electronic medical record review for substance abuse in the previous 6 months                                  |
| • Comorbid metastatic cancer  | • Electronic medical record review   |
| • Diagnosis of obesity hypoventilation syndrome                           | • Inpatient or outpatient diagnostic code (ICD9 278.03, ICD10 E66.2) or (BMI >=45 and diagnostic codes for COPD) |
| • Nursing home resident   | • Electronic medical record review or self-report  |
| • Heart or lung transplant or LVAD  | • Electronic medical record review or self-report  |
| • Participation in the intervention arm of the CASA trial, COMIRB 11-0969 | • Electronic medical record review   |
| • Enrolled in palliative care, hospice or home based primary care         | • Electronic medical record review or self-report  |
| • Prisoner  | • Electronic medical record  |
| • Pregnant  | • Electronic medical record or self-report   |

\*ICD-9 code definitions for CHF (428.XX) validated in Go et al; ICD-9 code definitions for COPD (491.XX, 492.XX, 493.2, 496.XX) validated in Au et al and the corresponding ICD-10 codes

\*\*ICD-9 code definitions for ILD: 515, 516.30, 516.31, 516.32, 516.34, 516.37 and the corresponding ICD-10 codes

†ICD-9 codes for dementia (290.0-290.43, 291.2, 046.1, 294.0, 294.1x, 294.2x, 294.8, 331.0, 331.1x, 331.2, 331.6, 331.7, 331.82, 331.89, 331.9) from Taylor et al and Bharmal et al and the corresponding ICD-10 codes

Patients with CHF, ILD, or COPD in both the PSVAHCS and VA ECHCS will be identified electronically by staff at the VA ECHCS site using validated combinations of diagnostic codes. The Care Assessment Need Palliative care to improve quality of life in CHF and COPD\_Protocol\_v\_05.08.2018

(CAN) score will be used to define a population at increased risk for hospitalizations or death that is likely to need the palliative care intervention because of increased illness severity. The CAN is a VA-developed prognostic tool that was created to help primary care proactively identify and manage at risk Veterans on a population level. We will collect the CAN score on all potential subjects with a diagnosis of CHF, COPD, or ILD as defined in Table 1. A CAN score of  $\geq 80$  for those with CHF or COPD was chosen in consultation with the VA Central Offices of Primary Care and Palliative Care. Preliminary studies identified 5,951 Veterans total at both sites with CHF or COPD and a CAN score of  $\geq 80$ . The CAN score may not be as valid for the small number of patients with ILD, thus we will not use it as an eligibility criterion.

To enroll a sample with poor quality of life who is appropriate for the intervention, potential participants will need to report a Functional Assessment of Chronic Illness Therapy-General (FACT-G) score  $\leq 70$  and be bothered by one of the intervention target symptoms. The FACT-G is a widely-used, valid, reliable quality of life measure that is the primary outcome in this study. It measures physical, social/family, emotional, and functional well-being. A score of  $\leq 70$  identifies poor quality of life as validated by declining performance status and increasing disease burden.

Given the intervention delivery model whose purpose is to integrate palliative care into chronic care, a provider (ideally the PCP) must be willing to work with the intervention team. In prior studies, all PCPs were willing to work with the team. The intervention was developed in English for adults and the majority of the study instruments have been validated only in English. As the intervention is provided by phone, participants must have phone access. Potential participants who have a previous diagnosis of dementia will be excluded because the intervention requires participation in counseling that was not developed for people with dementia, and most of the questionnaires were not validated in persons with dementia. Subjects who have problems with active substance abuse, defined as a substance abuse documented in EMR in the previous 6 months (cannabis will be allowed) are unlikely to participate in the regular follow up phone calls or respond to the intervention and will be excluded. Subjects with comorbid metastatic cancer are excluded because this study focuses on CHF, ILD, and COPD rather than cancer palliative care. Those with a diagnosis of obesity hypoventilation syndrome, or those at high risk for obesity hypoventilation syndrome (BMI  $\geq 45$  and diagnostic codes for COPD), are excluded as we do not think this intervention will be helpful to them. Those with a heart or lung transplant or left ventricular assist device (LVAD) will be excluded because they already receive substantial psychosocial care and resources. Those receiving palliative care, hospice and home-based primary care will be excluded as they are likely to be receiving services similar to what is provided in the intervention. We will exclude those who participated in the intervention arm of the CASA trial (COMIRB #11-0969) as they have received some components of the intervention in this trial. Finally, nursing home residents will be excluded since this study is focused on outpatient care. Competence for study participation will be evaluated by potential participants' ability to explain to study personnel the goals of the study, requirements of study participation, and potential risks and benefits.

**Patient interviews:** After the outcome measurement at 6 months, we will conduct interviews with Veterans randomized to the intervention arm to ask their opinions on the helpfulness of the intervention. We will interview a subset of patients completing the intervention every 6 months in order to account for potential differences over time (e.g., intervention provider experience).

**Intervention personnel:** All intervention personnel will be invited to participate.

**Primary care providers whose patients have received the intervention:** Providers who have patients who have completed the intervention will be invited to complete a brief survey.

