**I. Hypotheses and Specific Aims:**

We will conduct a two site randomized clinical trial (VA Eastern Colorado Health Care System [VA ECHCS] and VA Puget Sound [PSVAHCS]) to determine whether an intervention to improve symptoms and to help Veterans adjust to living with Chronic Heart Failure (CHF), Chronic Obstructive Pulmonary Disease (COPD) and Interstitial Lung Disease (ILD) improves quality of life. The intervention will also help Veterans communicate preferences for treatment with their providers. The intervention involves routine clinical care and no experimental drugs or devices. The results will be directly relevant to Veterans who suffer with these illnesses and their families, as well as to providers, leaders in VA Central Office, and other researchers. Furthermore, this study will generate information that supports the broader dissemination and implementation of the intervention and informs the development of future palliative care and team-based interventions in the VA. Specific aims include:

**Aim 1:** Determine the effect of the intervention on (a) quality of life as a primary outcome, and (b) depression, symptom burden, advance care planning communication and documentation, disease-specific health status, emergency department visits, hospitalizations, and mortality as secondary outcomes.

**Aim 2:** Examine the implementation of the intervention.

**Aim 2a:** Assess the degree, barriers, and facilitators of implementation of various intervention components. Identify which intervention components and processes are most critical from the perspectives of patients, intervention team members, and primary care providers whose patients received the intervention.

**Aim 2b.** Evaluate the resources (e.g., personnel time and other costs) associated with the intervention, and estimate the resources needed for implementation and maintenance of the intervention in other VA settings.

The brief study title is Advancing Symptom Alleviation with Palliative Treatment (ADAPT) and will be used with participants as it provides a simple acronym.

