15. Telephone Interview for Cognitive Status (TICS): The Telephone Interview for Cognitive Status is an 11-item verbally administered test of cognitive status. The TICS takes approximately 4 minutes to administer and assesses memory and other cognitive functions. The TICS was originally developed to discriminate between cognitive normals and dementia patients and has demonstrated good sensitivity and specificity when discriminating between normals and individuals with mild cognitive impairment. The TICS will be used as a covariate in the analyses.

16. Satisfaction surveys: Satisfaction with health care and the study will be assessed. Questions were adapted from the CANHELP Questionnaire.

**Aim 2a:** We will conduct a mixed method (i.e., combination of quantitative and qualitative) evaluation to assess intervention implementation.

Intervention database: The intervention database will be used to track intervention content and processes.

Brief patient interviews: After the 6 month outcome measurement, we will conduct interviews with Veterans randomized to the intervention arm to ask for their feedback on the intervention.

Intervention Close Out Summary: The intervention team will complete an Intervention Team Intervention Close Out Summary on each Veteran once they complete the intervention.

Focused Group Discussion with Intervention Team: We will conduct structured group discussions with intervention team members at the completion of the project intervention period to debrief about how the intervention was implemented.

Surveys of PCPs: We will administer a brief survey to all PCPs who have patients who have completed the intervention.

**Aim 2b:** We will evaluate the resources and costs to implement and maintain the intervention. Data for the *costs to implement* (i.e., start-up costs) and the *cost to maintain* the intervention will be collected separately. At a minimum, the costs to implement will include personnel training, database development; the costs to maintain will include identification of eligible Veterans and personnel time to provide the intervention (e.g., patient visits/phone calls; team meetings; communication/coordination with PCPs).

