**Table 6. Intervention implementation (Aim 2a) objectives, data collection, and analytic frameworks**

Objective	Data Source	Sample Size	Analytic Framework
Assess intervention component implementation	Intervention database	150	Quantitative : descriptive statistics by site and illness of the variability in "dose" and content of the delivered intervention
Identify critical intervention components and processes and facilitators/barriers to intervention implementation	Brief patient interviews	100	Qualitative analysis of data using the following CFIR* Domains, Constructs , allowing for emergence of new codes/ideas
	Intervention close out summary	150	Intervention Characteristics Relative advantage, complexity, cost, design quality and packaging
	Focused group discussion with intervention team	1-2	Characteristics of Individuals Knowledge & beliefs about Intervention
	Survey of PCPs whose patients have received the intervention	150	Outer Setting Patients' Needs and Resources Inner Setting Implementation climate, relative priority, readiness for implementation

\*CFIR, Consolidated Framework for Implementation Research

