differences over time (e.g., intervention provider experience). We will seek variability in the sample we interview (e.g., by sampling from both study sites and sampling patients who benefit the most and least from the intervention based on changes in the FACT-G score at 6 months or participant ratings of helpfulness). Interviews will be audio-recorded using a secure recording mechanism or an audio recording device. Detailed notes will be taken during the interviews. Interviews will be transcribed verbatim by VA contracted transcription service or a member of the study team. All interviews will be de-identified and all PHI/PII will be removed before transcribed.

***Intervention Close Out Summary:*** This 1-page summary form will capture information from intervention providers on what worked well and not so well with components of the intervention, what was missing, and whether the patient engaged in and followed up with behavioral changes.

***Focused Group Discussion with Intervention Team:*** The goal of this discussion is to elicit intervention team views about what worked well; what parts of the intervention might be streamlined, dropped or enhanced; and their views about patient, family caregiver, and PCP receptivity and responsiveness. A qualitative researcher will lead these focused group discussions which will be recorded and transcribed

***Surveys of PCPs:*** Using a combination of rating scales and a few open-ended questions, the goal of these surveys is to efficiently identify strong positive or negative opinions about the usefulness of different intervention components, integration of the intervention into work flow, and the perceived impact of the intervention on quality of care. We will also ask for their insights into ways to sustain and spread the intervention to other urban and rural VA sites. The questions were selected to explore specific CFIR constructs of importance. Providers will complete the survey via phone, in-person, or via e-mail.

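### As worded, three of the five Aim 2a data sources are triggered by completing the intervention, so a study of barriers has no set route to the views of Veterans who stop early or, on their account, of their PCPs

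*Protocol*

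**What the plan says.** Section I of the protocol gives the objective of Aim 2a: "Assess the degree, barriers, and facilitators of implementation of various intervention components". The rationale for Aim 2 in section II adds that, should the intervention not succeed, this aim is meant to inform later implementation of similar programmes.

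Five data sources serve the aim: an intervention database, patient interviews, a close-out summary, a group discussion with the intervention team, and a PCP survey. Three have a rule that refers to completion:

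- **Interviews** (section IV.B, repeated in IV.D): "We will interview a subset of patients completing the intervention every 6 months in order to account for potential differences over time". They take place after the 6-month outcome measurement.
- **Close-out summary** (section IV.A): "The intervention team will complete an Intervention Team Intervention Close Out Summary on each Veteran once they complete the intervention".
- **PCP survey** (section IV.A, with the same condition in IV.B): "We will administer a brief survey to all PCPs who have patients who have completed the intervention".

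Other wording is wider. Section IV.B also states "we will conduct interviews with Veterans randomized to the intervention arm to ask their opinions on the helpfulness of the intervention", and Table 6 lists a "Survey of PCPs whose patients have received the intervention". The SAP covers only the Aim 1 analysis and does not settle the matter.

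**The concern.** Veterans who disengage are a natural source of information on barriers. If completion is the entry condition, the people who could say why they stopped are left out by design, and the sample leans towards patients who engaged. Section IV.C in fact expects good interview uptake because those approached will already have taken part. The findings could then make the intervention look more acceptable, and its components easier to deliver, than they were.

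The PCP's side matters too. Section II attributes the limited results of the most promising earlier study to providers often not acting on palliative care recommendations. PCP views on patients who dropped out of contact are therefore among the more useful data this aim could collect.

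**Working it through.** There is no planned figure to reproduce; the question is who can enter each source. Setting the rules side by side for an intervention-arm Veteran who stops contact early:

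| Source | Stated rule | Early stopper, rule followed literally |
|---|---|---|
| Intervention database (IV.D) | Visit number, duration and content for each patient | Included, but records delivery only |
| Team discussion (IV.D) | Team's views, including on patient and PCP receptivity | Covered, but only through the team |
| Close-out summary (IV.A) | Once the Veteran completes | No form |
| Interview (IV.B, IV.D) | Subset of completers, after month 6 | Not planned |
| PCP survey (IV.A, IV.B) | PCPs with a patient who completed | Not triggered by this patient |

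**Does the sampling for variability close the gap?** Section IV.D seeks variety across sites and by "sampling patients who benefit the most and least from the intervention based on changes in the FACT-G score at 6 months", or by rated helpfulness. This reaches patients who gained little. A patient with no 6-month FACT-G has no change score, and one with no helpfulness rating cannot be picked on that basis either. The criteria are given as examples, so early stopping could be added, but it is not listed.

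**Is completion defined?** No. Section IV.C plans about 6 nurse visits and 6 social worker visits at 2 per month, that is 6 / 2 = about 3 months, and lets the number vary. Completion could mean a full course or simply the end of the intervention period. Two sites, or two staff members, could apply it differently.

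**Do the planned counts reveal the intended frame?** They do not. Table 6 lists 150 close-out summaries against 200 intervention patients (400 randomized 1:1), or 150 / 200 = 75%. That might suggest a completer frame, but Table 6 gives the same 150 for the database, which covers every patient. Interviews are put at no more than 120 in section IV.C (120 / 200 = 60%) and at 100 in Table 6 (100 / 200 = 50%).

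**Can the size be computed?** No. The Sample Size text expects 5% deaths (0.05 x 200 = 10 intervention patients) and 15-20% with missing outcomes (0.15 x 200 = 30 to 0.20 x 200 = 40). These are losses of outcome data, and they include people who merely left surveys unfinished. A Veteran can finish the visits at about month 3 and miss month 6, or stop the visits and still answer at month 6. All that can be said is that each percentage point of early stopping is 2 of the 200 patients.

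**The case against.** The strongest reply is that completion was meant loosely. Dose is allowed to vary, so there is no fixed course to fail. The close-out form is meant for each Veteran and records "whether the patient engaged in and followed up with behavioral changes", a field that anticipates poor engagement. Several places refer to Veterans randomized to the intervention, or to PCPs whose patients received it. This stands as far as it goes: the documents do not show that the team intends to leave early stoppers out. But the sentences that say who is sampled, who gets a form and who is invited use completion, and no text provides for early stoppers. Staff who skipped them would be following the protocol.

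Four stronger readings are tempting and are not supported:

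- *That Aim 2a draws only on completers.* Two of the five sources have no such limit, and the wider wording makes the other three ambiguous.
- *That it misses patients for whom the intervention failed.* Not benefiting differs from not completing, and section IV.D deliberately samples those who benefited least.
- *That a skipped month 6 or unsigned orders removes a patient from all three sources.* The form and the survey depend on the intervention, so a skipped month 6 costs at most the interview. Section IV.C leaves signing to the providers' discretion while the team delivers the non-drug care at once, so unsigned orders do not prevent completion.
- *That the expected 15-20% missing outcomes measures the gap.* It is not a stopping rate. Nor would a calculated bias in how often a barrier is reported be apt, since the interviews seek themes until saturation and do not estimate prevalence.

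**Conclusion.** The point holds as a matter of the sampling frame. Read literally, the protocol gives early stoppers no close-out form and no planned interview, and does not survey their PCPs on their account; a PCP with another patient who completed is still surveyed. For early stoppers the barriers objective then rests on delivery records and the team's impressions.

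This assumes that completion means more than the passing of the intervention period. If the team reads it as the end of contact for any reason, the close-out and PCP gaps largely close in practice, though the wording still needs to say so and the interview criteria still do not name early stoppers. How many patients are involved is unknown. The effect is confined to Aim 2a, a descriptive aim; the Aim 1 comparison is untouched. It is worth correcting because the remedy uses existing instruments and is cheap.

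**What to change.** Use one frame, all Veterans randomized to the intervention, wherever sections IV.A, IV.B and IV.D describe these three sources, and define completion if the term is kept. Then:

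1. Fill in the one-page close-out summary for every intervention patient when intervention contact ends for any reason, and record that reason.
2. Invite the PCPs of all intervention patients to the survey.
3. Add early stopping and non-engagement to the variability criteria in section IV.D, so that some of the interviews already planned go to these patients. No fixed quota is needed.

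Keep the interviews after the 6-month outcome measurement or, for those who miss it, after its window has closed. Interviewing people at the moment they stop would put an evaluative contact, in one arm only, ahead of a self-reported primary outcome among patients who can tell which arm they are in.

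The cost is a few more one-page forms and surveys, some refusals among early stoppers, and slightly fewer interviews with completers. Interview consent is already taken at enrollment (section IV.C), and the planned number of interviews need not change.
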